9.5 Severity of Adverse Events

The severity of AEs will be graded from 1 to 5 according to NCI Common Terminology Criteria for Adverse Events (CTCAE) version 5.0 general guidelines (see Table 4). An AE that is assessed as severe should not be confused with an SAE. Severity is a category utilized for rating the intensity of an event; both AEs and SAEs can be assessed as severe.

Table 4: CTCAE General Categories

Grade	Clinical Description
1	Mild; asymptomatic or mild symptoms; clinical or diagnostic observations only; intervention not indicated
2	Moderate; minimal, local or noninvasive intervention indicated; limiting age- appropriate instrumental activities of daily living
3	Severe or medically significant but not immediately life-threatening; hospitalization or prolongation of hospitalization indicated; disabling; limiting self-care activities of daily living
4	Life-threatening consequences; urgent intervention indicated
5	Death related to AE

9.6 Reporting Serious Adverse Events

A serious adverse event (SAE) is any untoward medical occurrence that at any dose:

- Results in death
- Is life-threatening (NOTE: The term "life-threatening" in the definition of "serious" refers to an event/reaction in which the subject was at risk of death at the time of the event/reaction; it does not refer to an event/reaction which hypothetically might have caused death if it were more severe)
- Requires inpatient hospitalization or results in prolongation of existing hospitalization

Confidential Page 42 of 64

NOTE: Prolongation of existing hospitalizations for social or situational reasons will not be considered an SAE (e.g., waiting for placement or availability in a step-down unit or rehabilitation facility, no place to stay, etc.).

- Results in persistent or significant disability/incapacity
- Is a congenital anomaly/birth defect
- Is a medically important event or reaction

Medical and scientific judgment should be exercised in deciding whether reporting is appropriate in other situations, such as important medical events that may not be immediately life threatening or result in death or hospitalization but may jeopardize the subject or may require medical or surgical intervention to prevent one of the other outcomes listed in the above definition. These should also usually be considered serious. Examples of such medical events include cancer, allergic bronchospasm requiring intensive treatment in an emergency room or at home, blood dyscrasias or convulsions that do not result in hospitalizations, or the development of drug dependency or drug abuse.

Initial Reports

All SAEs occurring from the time of informed consent until Day 28, regardless of causality or relationship to treatment, must be reported to Medpace Clinical Safety within 24 hours of the knowledge of the occurrence. After Day 28, any SAE that the Investigator considers related to IP must be reported to Medpace Clinical Safety or the Sponsor/designee.

To report the SAE, the Investigator/designee completes the SAE form electronically in the electronic data capture (EDC) system for the study. When the form is completed, Medpace Safety personnel will be notified electronically by the EDC system and will retrieve the form.

If the event meets serious criteria and access to the EDC system is not possible, send an e-mail to Medpace Safety at [contact] or call the Medpace SAE reporting line (phone number listed below), and fax or e-mail the completed back-up paper SAE reporting form to Medpace (fax number listed below) within 24 hours of awareness. When the EDC system becomes available, the SAE information must be entered within 24 hours of the system becoming available.

Company: Medpace

Attention: Medpace Clinical Safety

Email: [contact]

Phone: North America: [contact], dial 3 or [contact], dial 3

Europe: [contact]

Fax: North America: [contact] or [contact]

Europe: [contact]

Confidential Page 43 of 64

The initial notification will include at least a description of the event and the subject identification number. This information should be supported as needed with written copies of hospital case reports, autopsy reports, and other documents when applicable.

Follow-up Reports

The Investigator must continue to follow the subject until the SAE has subsided or until the condition becomes chronic in nature, stabilizes (in the case of persistent impairment), or the subject dies.

Within 24 hours of receipt of follow-up information, the Investigator must update the SAE form electronically in the EDC system for the study and submit any supporting documentation (e.g., patient discharge summary or autopsy reports) to Medpace Clinical Safety via fax or e-mail. If access to the EDC system is not possible, refer to the procedures outlined above for initial reporting of SAEs.

IEC/IRB and Regulatory Reporting

The Investigator should notify the IEC/IRB of SAEs occurring at the site in accordance with local procedures.

The Sponsor has a legal responsibility to notify the appropriate regulatory authorities about the safety of any test drug. Accordingly, prompt notification of any adverse events by Investigators to the Sponsor is required. The reporting of SAEs will be conducted in accordance with ICH, Good Clinical Practice (GCP), and local regulatory guidelines.

9.7 Pregnancy Reporting

If a subject becomes pregnant before Day 28, the subject will be followed per the schedule of assessments for the full study follow-up period (6 months; see Table 1), and in addition, the pregnancy should be followed by the Investigator until completion.

A pregnancy is not considered to be an AE or SAE; however, it must be reported to Medpace Clinical Safety within 24 hours of knowledge of the event. Medpace Clinical Safety will then provide the Investigator/site the Exposure In Utero (EIU) form for completion. The Investigator/site must complete the EIU form and fax or email it to Medpace Clinical Safety.

If the female partner of a male subject becomes pregnant before Day 28, the Investigator should notify Medpace Clinical Safety as described above.

The pregnancy should be followed until the outcome of the pregnancy, whenever possible. Once the outcome of the pregnancy is known, the follow-up EIU form should be completed and faxed or emailed to Medpace Clinical Safety. If the outcome of the pregnancy meets the criteria for immediate classification as an SAE (i.e., postpartum complication, spontaneous abortion, stillbirth, neonatal death, or congenital anomaly), the Investigator should follow the procedures for reporting an SAE.

Confidential Page 44 of 64

9.8 Expedited Reporting Requirements

9.8.1 Suspected Unexpected Serious Adverse Reaction

A suspected unexpected serious adverse reaction (SUSAR) is considered any SAE for which there is a reasonable possibility that the IP caused the SAE and is considered "unexpected" i.e., not listed in the Reference Safety Information section of the Investigator's Brochure, or is not listed at the specificity or severity that has been observed in an adverse reaction, the nature or severity of which is not consistent with the applicable product information.

The Sponsor or designee will report all relevant information about fatal or life-threatening SUSARs or IND safety reports (INDSRs) as soon as possible to the FDA and applicable competent authorities, and in any case no later than 7 calendar days after knowledge by the Sponsor or designee of such a case. Relevant follow-up information will subsequently be communicated as soon as the information is available but no later than 15 calendar days after the Sponsor or designee receives the information.

All other SUSARs or INDSRs will be reported to the FDA and applicable competent authorities as soon as possible but within a maximum of 15 days of first knowledge by the Sponsor or designee. The Sponsor or designee will also inform all Investigators of SUSARs or INDSRs as required.

Confidential Page 45 of 64

10 STATISTICS

A separate Statistical Analysis Plan (SAP) will provide additional details for statistical analyses and data displays.

10.1 Analysis Populations

The Safety Population will include all subjects who are randomized and receive at least 1 dose of IP (FDY-5301 or placebo).

The Intent-to-Treat (ITT) Population will include all randomized subjects.

The Per-Protocol (PP) Population will include all subjects in the ITT Population who meet the following criteria:

- have met all inclusion and no exclusion criteria
- receive at least 1 dose of IP (FDY-5301 or placebo)
- have CPAx total score at Day 10 or hospital discharge, whichever occurs first
- have interpretable organ dysfunction total TTR data
- do not have any major protocol deviations that may impact the efficacy endpoints

The PK Population will include all subjects who are enrolled and receive at least 1 dose of IP and have at least 1 evaluable PK sample.

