10.2.2 Handling of Missing Data

CPAx total scores will be analyzed using ANCOVA on observed data. To assess the impact of missing data, multiple imputation will used as supplementary analysis. Tipping-point analysis will also be performed. Details will be described in the SAP.

For organ dysfunction total TTR, no imputation will be performed. For all other endpoints, missing observations will be excluded from analysis.

Descriptive summaries of efficacy and safety measures will be based on observed data.

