10.2.4 Efficacy Analyses

The ITT Population will be used for all efficacy analyses. The PP Population will be used as a sensitivity analysis to assess robustness of the efficacy results.

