10.2.4.2 Secondary Efficacy Analysis

For secondary endpoints, a sequential analysis will be performed. The continuous secondary efficacy endpoints of MRC-SS and worst SOFA score will be analyzed with an ANCOVA model similar to the one described for the primary endpoint of CPAx total score. The secondary endpoint of overall survival at Day 28 will be analyzed using a Kaplan-Meier approach and a log-rank test, similar to the methodology described for the primary endpoint of organ dysfunction total TTR until Day 28.

The pooled treatment groups versus placebo will be analyzed first, followed by a step-down analysis.

The p-values, least-squares means, standard errors, and the 2-tailed 95% confidence intervals for the treatment groups and placebo group will be presented, where appropriate.

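### The one per-protocol set requires a Day 10 (or discharge) CPAx score, so the PP analysis of Day 28 survival leaves out almost every death before Day 10 and cannot test an early mortality difference

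*Combined protocol and SAP*

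**What the plan says.** Section 10.1 gives one PP definition for the whole trial. Besides eligibility, at least one dose and no major deviation affecting efficacy, it sets two data-availability conditions: subjects must "have CPAx total score at Day 10 or hospital discharge, whichever occurs first" and must "have interpretable organ dysfunction total TTR data". No endpoint has its own PP set.

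Section 10.2.4 states that "The ITT Population will be used for all efficacy analyses", and Section 10.1 that "The Intent-to-Treat (ITT) Population will include all randomized subjects". Section 10.2.4 then adds: "The PP Population will be used as a sensitivity analysis to assess robustness of the efficacy results". That sentence is not limited to CPAx.

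The efficacy endpoints are CPAx and TTR (Section 10.2.4.1) and MRC-SS, worst SOFA and Day 28 survival (Section 10.2.4.2). For survival: "The secondary endpoint of overall survival at Day 28 will be analyzed using a Kaplan-Meier approach and a log-rank test". For the other two: "The continuous secondary efficacy endpoints of MRC-SS and worst SOFA score will be analyzed with an ANCOVA model".

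On missing data, Section 10.2.2 says "CPAx total scores will be analyzed using ANCOVA on observed data" and that TTR will not be imputed. Neither statement gives a value or a rule for death. Section 6.1.11 dates hospital discharge by clearance to leave.

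**The concern.** Section 6.1.11 ties discharge to clearance to leave, so an in-hospital death is not a discharge. A subject who dies in hospital before Day 10 therefore has neither a Day 10 nor a discharge CPAx score, and no score is assigned to death. That subject falls outside the PP set. Apart from subjects scored at an early live discharge who then die, the PP survival curve is flat to Day 10 in every arm by construction.

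A PP set should remove departures from the protocol. Death is not a departure, and for survival it is the outcome itself. If ITT showed an early excess or deficit of deaths, a PP result showing no difference could be read as evidence against it, when it would only reflect who was admitted to the set.

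The same condition removes subjects who have usable SOFA, TTR or survival data but no CPAx score. Those who die early are likely to have high worst SOFA scores and no recovery, so the loss need not be neutral.

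**Working it through.** **Reading of the rules.** For a death in hospital before Day 10:

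| Rule | Result |
|---|---|
| CPAx at Day 10 (10.1) | not met: dead |
| CPAx at discharge (10.1, 6.1.11) | not met: never cleared for discharge |
| CPAx value assigned to death (10.2.2) | none given |
| Use of the PP set (10.2.4) | efficacy results without limit |

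Section 4.2 excludes only those likely to die within 48 hours of screening, so deaths between then and Day 10 remain possible. Deaths after Day 10 stay in PP if the other conditions are met.

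**The plan's own figures.** No stated figure concerns the PP set. The sample-size figures in Section 10.2.7 do reproduce:
- Evaluable: 84 × 0.85 = 71.4, taken as 71; 71 × 3 = 213.
- CPAx, 71 versus 142: SE = 12 × √(1/71 + 1/142) = 1.744; 6/1.744 − 1.96 = 1.48; power 93% (stated >90%).
- TTR: √(213 × 1/3 × 2/3) × |ln 0.70| − 1.96 = 0.49; power 69% (stated about 70%).

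**Inputs for size.** 84 placebo and 168 pooled active (Section 10.2.7). All mortality rates and timings below are assumptions.

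**Deaths removed, 10% Day 28 mortality.** 252 × 0.10 = 25.2 deaths. If 40% to 80% fall before Day 10, PP loses 10.1 to 20.2 of them.

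**Survival, worst case.** Day 28 mortality is 8% placebo and 16% active, with 2.4% of each arm dying after Day 10. Early mortality is then 5.6% and 13.6%.
- ITT deaths: 84 × 0.08 + 168 × 0.16 = 33.6.
- PP deaths: 252 × 0.024 = 6.0.
- PP mortality = late / (1 − early): 0.024/0.944 = 2.5% and 0.024/0.864 = 2.8%.
- Simulated chance that the log-rank test shows the harm: about 41% in ITT, about 1% in PP.

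**Survival, equal early share.** Same totals, with a fraction f of deaths before Day 10 in each arm. PP mortality = m(1 − f)/(1 − mf), and hazard ratio = ln(1 − active)/ln(1 − placebo). In ITT this is ln 0.84 / ln 0.92 = 2.09.

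| f | PP placebo | PP active | PP hazard ratio | Deaths left | PP power |
|---|---|---|---|---|---|
| 0.3 | 5.7% | 11.8% | 2.12 | 23.5 | 31% |
| 0.5 | 4.2% | 8.7% | 2.14 | 16.8 | 22% |
| 0.7 | 2.5% | 5.4% | 2.16 | 10.1 | 12% |

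ITT power is about 41% in each row (powers by simulation).

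**Survival, early benefit.** Death by Day 10 is 12% placebo and 6% active, then 5% of survivors in both arms. ITT mortality is 1 − 0.88 × 0.95 = 16.4% and 1 − 0.94 × 0.95 = 10.7%, hazard ratio 0.63. PP shows 5% and 5%, hazard ratio 1.0. PP therefore erases a wholly early benefit just as it erases a wholly early harm.

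**Worst SOFA.** Assume mean 14 in early deaths and 8 otherwise, with early death 15% placebo and 5% active. ITT means are 0.15 × 14 + 0.85 × 8 = 8.9 and 0.05 × 14 + 0.95 × 8 = 8.3, a difference of −0.6 (simulated −0.58). PP: 0.01. With 10% early death in both arms: 0.03 in ITT and 0.01 in PP.

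**TTR.** Planned medians of 7 and 4.9 days, simulated recovery rate ratio, active to placebo:

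| Early death, placebo / active | ITT, deaths unrecovered to Day 28 | ITT, censored at death | PP |
|---|---|---|---|
| 10% / 10% | 1.26 | 1.42 | 1.44 |
| 5% / 15% | 0.97 | 1.31 | 1.44 |

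The gap between ITT and PP thus depends on balance of early mortality and on the handling of death.

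**The case against.** The strongest reply is that little hangs on this set. ITT is the analysis set for all efficacy analyses, and PP decides nothing. Early deaths stay in ITT survival, are reported as serious adverse events to Day 28, and are open to review by the safety monitoring committee. A reader might infer that the plan conceals an early mortality harm. The documents do not support that: the blind spot lies inside one supplementary analysis.

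Second, Section 10.2.4 names no endpoint and does not expressly promise a PP log-rank test for survival. The two data conditions match the two co-primary endpoints, which suggests they were written with those in mind. That is fair, but the sentence covers the efficacy results without limit and survival is one of them.

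Third, a reader might infer that PP cannot check SOFA or TTR either. That goes too far. With balanced early mortality the SOFA contrast is nearly unchanged, and TTR is nearly unchanged if deaths are censored. The documents do not state the TTR rule for death.

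Fourth, the worst-case figures follow from placing the entire mortality difference before Day 10. With an equal early share, PP keeps the direction and size of the effect and mainly loses events. This stands, and both cases must be shown.

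Fifth, Section 10 defers detail to a separate SAP, which is not in the text reviewed and might restrict PP use by endpoint. It cannot be relied on to cure an explicit population definition in the protocol.

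**Conclusion.** Wrong as written, minor, sensitivity analysis only. That PP survival is conditioned on its own outcome follows from the definitions alone and needs no mortality assumption. As a result, the PP analysis cannot confirm or refute an early mortality difference in either direction.

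Its size does rest on assumptions, because the documents give neither the rate nor the timing of deaths. At 8% versus 16% Day 28 mortality, it ranges from near-complete masking, when the difference is all early, to a hazard ratio that is preserved with roughly a quarter to 70% of the power lost, when the early share is equal (41% down to 31% and 12%). For worst SOFA and TTR the check is weakened under unbalanced early mortality, and for TTR also according to how death is handled.

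**What to change.** In Section 10.1, define the general PP set by eligibility, dosing and absence of major protocol deviations. Make the two data-availability conditions endpoint-specific: the CPAx condition for the PP analysis of CPAx only, the TTR condition for the PP analysis of TTR only, and neither for overall survival, worst SOFA or MRC-SS. Carry the same wording into the SAP.

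The cost is one text edit. PP denominators will differ by endpoint and should be shown in each table. No new data are needed and no primary analysis changes.

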10.2 Statistical Methods

10.2.1 Demographic and Baseline Characteristics

Demographic and baseline characteristics will be summarized using descriptive statistics by treatment group. Subject disposition will be summarized by treatment group. All subjects enrolled will be included in a summary of subject disposition.

10.2.2 Handling of Missing Data

CPAx total scores will be analyzed using ANCOVA on observed data. To assess the impact of missing data, multiple imputation will used as supplementary analysis. Tipping-point analysis will also be performed. Details will be described in the SAP.

For organ dysfunction total TTR, no imputation will be performed. For all other endpoints, missing observations will be excluded from analysis.

Descriptive summaries of efficacy and safety measures will be based on observed data.

10.2.3 Safety Analyses

The Safety Population will be used for all safety analyses.

Confidential Page 46 of 64

All adverse events reported in this study will be coded using the Medical Dictionary for Regulatory Activities (MedDRA).

Safety analysis includes summary for AEs, TEAEs, SAEs, clinical laboratory assessments, and 12-lead ECGs. No statistical testing will be conducted for safety endpoints.

All clinical safety and tolerability data will be listed for each subject. Hematology, clinical chemistry, and thyroid function will be analyzed by group mean and outlier analyses.

AEs, TEAEs, and SAEs will be summarized by group, severity, and relationship to the IP. Other safety measures will be summarized descriptively by treatment and visit.

10.2.4 Efficacy Analyses

The ITT Population will be used for all efficacy analyses. The PP Population will be used as a sensitivity analysis to assess robustness of the efficacy results.

10.2.4.1 Primary Efficacy Analyses

There are two co-primary efficacy endpoints defined in this study:

- CPAx total score at Day 10 (or at hospital discharge, whichever occurs first)
- Organ dysfunction total TTR until Day 28

Both primary endpoints will be compared across treatment groups and tested at the 0.05 level of significance and, by convention, both endpoints must demonstrate statistical significance (i.e., $p \le 0.05$) to conclude treatment superiority for regulatory purposes.

For the first primary efficacy endpoint, CPAx total score at Day 10 (or at hospital discharge, whichever occurs first), the following hypothesis will be tested:

$$H_0$$
: $\mu_{Tp} = \mu_p \ v. s. H_a$: $\mu_{Tp} \neq \mu_p$

Where μ_{Tp} , μ_p denote the CPAx total score at Day 10 (or at hospital discharge, whichever occurs first) in the pooled treatment group (FDY-5301 1 mg/kg and FDY-5301 2 mg/kg combined) and placebo groups, respectively. As the primary analysis, the treatment comparison of the CPAx total scores will be performed using analysis of covariance (ANCOVA). The model will include CPAx total score at Day 10 (or at hospital discharge, whichever occurs first) as dependent variable treatment and stratification category (with or without presence of pelvic or lower limb fractures) as factors; and "baseline" CPAx (the first available datapoint) as a continuous covariate.

The p-values, least-squares means, standard errors, and the 2-tailed 95% confidence intervals for the treatment groups and placebo group will be presented.

Confidential Page 47 of 64

If the difference between the means of the pooled treatment group compared to the placebo group is statistically significant, a step-down procedure will be followed to test the individual FDY-5301 doses compared to placebo. The following testing order of doses will be used:

- 1) FDY-5301 2 mg/kg versus placebo
- 2) FDY-5301 1 mg/kg versus placebo

The same statistical method as for the comparison between the pooled treatment group and placebo will be used.

For the second primary efficacy endpoint, organ dysfunction total TTR, the time will be calculated as date of recovery minus date of treatment start plus 1 day. The time to recovery will be estimated using Kaplan-Meier methodology. The Kaplan-Meier curves will be plotted and the time to recovery will be compared using log-rank test at significance level 0.05. The pooled versus placebo and then step-down analysis procedure will be used.

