2 TRIAL OBJECTIVES AND ENDPOINTS

The purpose of the trial is to evaluate the efficacy, safety, and PK of FDY-5301 compared to placebo in major trauma ICU patients at risk of ICUAW.

Objectives	Endpoints								
Primary	Coprimary								
To assess the effect of FDY-5301 on muscle function and organ dysfunction in the major trauma ICU population	 Chelsea Critical Care Physical Assessment Tool (CPAx) total score at Day 10, or hospital discharge, whichever occurs first Organ dysfunction total time to recovery (TTR) until Day 28 								
Secondary	Secondary								
To assess the effects of FDY-5301 on other clinical outcomes in the major trauma ICU population	The secondary endpoints will be analyzed in the following sequence: • Medical Research Council Sum Score (MRC-SS) at Day 28 or hospital discharge, whichever occurs first • Worst Sequential Organ Failure Assessment (SOFA) score during ICU stay • Overall Survival at Day 28								
Safety	Safety								
To investigate the safety and tolerability of up to 7 daily bolus IV doses of FDY-5301 in the major trauma ICU population	Safety will be evaluated based on occurrence of or changes throughout the study in the following parameters: • Adverse events (AEs), treatment-emergent adverse events (TEAEs) and serious adverse events (SAEs) • Clinical laboratory assessments (hematology, clinical chemistry, and thyroid function tests) • 12-lead electrocardiogram (ECG) assessments								
Exploratory	Exploratory								
To assess the effects of FDY-5301 on skeletal muscle, muscle function, and other clinical outcomes and to investigate the PK of up to 7 daily bolus IV doses in the major trauma ICU population	 Overall survival at Month 3 and Month 6 from date of injury Time to successful ventilator extubation from time of first dose Time to hospital discharge from first hospital arrival time and time of first dose, and discharge disposition (e.g., home, home with community support, rehabilitation unit, or nursing home) 								

Confidential Page 22 of 64

- Incidence of sepsis through Day 28
- SOFA score and sub score components at Days 1, 3, 7, 14, 21, and Day 28 or ICU discharge, whichever occurs first
- CPAx total score and sub score components at Days 1, 3, 7, 10 (sub score components only), 14, 21, and Day 28 or hospital discharge, whichever occurs first

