5 STUDY SCHEDULE

The schedule of assessments for all clinical trial sites is listed in Table 1. The additional schedule of assessments for US clinical trial sites only is listed in Table 2.

All study visits will be calculated from time of first IP dose (Day 1). Month 3 and Month 6 visits will be calculated based on the calendar month (e.g., if Day 1 is February 15th, Month 3 would be May 15th and Month 6 would be August 15th).

Confidential Page 29 of 64

Table 1: Schedule of Assessments

Activity	Screening		In-Hospital										Follow Up Long Term Follow Up			
	J			Day 2ª	Day 3ª	Day 4ª	Day 5ª	Day 6ª	Day 7ª	Day 10ª	Day 14ª			Day 28 If Discharged Earlier	Month 3	Month 6
			(+/-) 24hrs of 1 st IP dose								(+/-) 1 day	(+/-) 1 day	(+/-) 1 day	(+) 2 weeks	(+/-) 1 week	(+/-) 2 weeks
Informed Consent	X											,				
Eligibility Criteria	X															
Estimated Height & Weight	X															
Medical History	X															
Demographics	X															
Physical Examination	X				X				X		X	X	X			
Serum Pregnancy Test	X															
Safety Laboratory Tests	X				X				X		X	X	X	X		
12-lead ECG		Randomization	XcXq		X				X		X		X			
TRISS		izat	X													
IP Administration		E	Χe	Χ ^f	Χ ^f	Χ ^f	Χf	Χ ^f	Χf							
CT Scan of Abdomen	Xa	pue								Xh						
SOFAi		8	X		X		à à		X		X	X	X			
Sit to Stand	26									Х	X	X	X		O.	
СРАх			X		X				X	Х	X	X	X			
MRC-SS							à à		å f				X			
Barthel Index													X		X	X
SF-36v2 Health Survey									à f				X		X	Х
Organ Dysfunction TTR			X	X	X	X	X	X	X	X	X	X	X			
Time of Extubation			X	X	X	X	X	X	X	X	X	X	X		DA .	
Occurrence of Sepsis			X	X	X	X	X	X	X	X	X	X	X			
Discharge & Disposition	2		X	X	X	X	X	X	X	X	X	X	X		X	Х
General Health Inquiry															X	X
Overall Survival	. 00		X	X	X	X	X	X	X	X	X	X	X	χj	X	X
Concomitant Medications	X		X	X	X	X	X	X	X	X	X	X	X	χj		
Adverse Events	X		X	X	X	X	X	X	X	X	X	X	X	χi		1

^aIf being discharged from hospital prior to Day 28, conduct all "Day 28 or Hospital Discharge if Earlier" assessments

ⁱConducted until ICU discharge only

^jMay be conducted by phone

Page 30 of 64

^bAssessments may be conducted up to 2 days prior to discharge if earlier than Day 28

^cUp to 12 hrs pre-dose

d Up to 4 hrs post-dose

^eAs soon as possible and within 48 hrs of FIRST hospital arrival time (i.e. immediately post injury)

f(+/-) 4 hrs using the time of day of first IP dose

^gOnly if performed as standard of care within 48 hrs of first hospital arrival and up to 24 hrs after first IP dose

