6.1.5 Chelsea Critical Care Physical Assessment (CPAx)

Trained site personnel will conduct the Chelsea Critical Care Physical Assessment (CPAx) per the study-specific Functional Assessments Manual. The CPAx is designed to measure functional recovery from critical illness. The CPAx includes the following 10 components:

- Respiratory function
- Cough
- Moving within bed
- Supine to sitting on the edge of bed
- Dynamic sitting
- Standing balance
- Sit to stand
- Transferring from bed to chair
- Stepping
- Grip strength

The CPAx components will be graded on a 6-point scale from dependent to independent (0 to 5). The individual values will be collated giving a total score out of 50.

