8.4 Preparation and Administration

The formulation has no preservative and is intended for single use only. Injection solutions will be prepared using aseptic technique and inspected prior to administration. The solution for injection is a clear, colorless solution with no particulate matter.

Preparation of the administered dose will be achieved by adjusting the volume of undiluted solution (calculation is based on IP concentration of 7.2 mg/mL) according to treatment assignment. Dosage is based on the subject's body weight (estimated or actual) at screening.

IP will be administered intravenously by a healthcare professional by bolus injection over no more than 10 minutes. Use of an infusion pump is acceptable provided it can administer the total volume in less than 10 minutes. IP may be administered through a central line as long as the line is flushed prior to and following injection. IP must be administered without mixing with any other IV drugs.

Confidential Page 39 of 64

The first IP administration must occur as soon as possible and within 48 hours of first hospital arrival time (i.e. in case of transfers, use time of arrival to first hospital immediately post injury) and then daily for up to 7 days at approximately the same time each day (±4 hours using the time of day of the first IP administration).

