10.2.7 Sample Size Determination and Power Calculations

Approximately 252 subjects will be randomized in a 1:1:1 ratio to receive either FDY-5301 1 mg/kg, FDY-5301 2 mg/kg, or placebo (i.e. 84 subjects per group).

With 252 subjects (with a drop-out rate of 15%, corresponding to 213 evaluable subjects), using a 2-sided significance level of 0.05 and placebo group mean in CPAx total score at Day 10 of 30, assuming a standard deviation of 12 (Corner 2015 and Raymond 2020), this would provide >90% power if there exists an improvement of 6 points in the CPAx total score in the pooled treatment group (either FDY-5301 1mg/kg or 2 mg/kg) compared with placebo group, (i.e. scores of 36 for FDY-5301 vs. 30 Placebo).

Given the assumption that median expected organ dysfunction recovery time is 7 days for the placebo group and the median expected organ dysfunction recovery time is 4.9 days for the pooled treatment group (Xiao 2011), i.e. an expected relative risk reduction of 30% and a 2-sided log-rank test at a significance level of 0.05, the study would have approximately 70% power if at least 213 events are observed (based on no subject being censored until Day 28).

Confidential Page 49 of 64

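### The CPAx ANCOVA sets no time limit on its baseline score, so an on-treatment score, or the outcome itself, can become the covariate; the likely bias toward zero is small and the wording fix is cheap

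*Combined protocol and SAP*

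**What the plan says.** Section 10.2.4.1 and the Synopsis give the same model for the first co-primary endpoint: Day 10 (or earlier discharge) CPAx on treatment and fracture stratum, with baseline "CPAx (the first available datapoint) as a continuous covariate". The protocol itself puts the word baseline in quotation marks. Neither place states a time window or a pre-dose condition.

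Section 2 lists the assessments as "CPAx total score and sub score components at Days 1, 3, 7, 10 (sub score components only", followed by later visits. Table 1 in Section 5 shows no CPAx at screening. The Day 1 column allows plus or minus "24hrs of 1 st IP dose", so even a Day 1 score may follow the first dose. Section 8.4 has the product given "daily for up to 7 days at approximately the same time each day", so Days 3 and 7 fall within the dosing period.

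On missing data, Section 10.2.2 says "CPAx total scores will be analyzed using ANCOVA on observed data", with multiple imputation as a supplementary analysis and a tipping-point analysis as well. It does not mention a missing baseline. Section 10 adds that "A separate Statistical Analysis Plan (SAP) will provide additional details"; that document is not in the supplied text.

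**The concern.** A covariate in an ANCOVA should not be affected by treatment. If part of the drug's effect is already in the covariate, the model attributes that part to baseline, and the treatment coefficient shrinks.

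The rule as written permits this in two ways. A subject with no Day 1 score takes the Day 3 or Day 7 score. A subject first scored on Day 10, or at an earlier discharge, has the same number as covariate and outcome. The schedule is tighter for other first measurements: the pre-dose ECG is limited to 12 hours before dosing, and the biomarker sample to between 24 hours before and 4 hours after the first dose. The covariate of a co-primary analysis has no such limit.

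What is at stake is the accuracy of the CPAx effect estimate and a clear statement of what it is adjusted for.

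**Working it through.** **Inputs from Section 10.2.7.** 213 evaluable of 252, allocated 1:1:1, so 142 pooled against 71 placebo; SD 12; difference 6; two-sided 0.05.

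**The plan's own figure.** SE = 12 × √(1/71 + 1/142) = 1.744. Then 6/1.744 = 3.44, and 3.44 − 1.96 = 1.48, which gives power of 93.1% (92.8% by noncentral t). The statement that "this would provide >90% power if there exists an improvement of 6 points" is reproduced. It uses no baseline covariate.

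**Inputs the documents do not give (assumed).**
- Share f with no Day 1 score: 5% to 50%.
- Day 1 to Day 10 correlation r: 0.5 to 0.8.
- Share of the effect present: 0/25/65% by Day 1/3/7.
- Subjects missing Day 1 are first scored on Day 3/7/10 in 60/35/5%.
- Placebo means on Days 1/3/7: 10/15/24.

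**Hand approximation.** With equal SDs, the adjusted effect is about 6 × (1 − r·f·e), where e is the average share of the effect already in the late score. Here e = 0.60×0.25 + 0.35×0.65 + 0.05×1 = 0.4275.

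| f | r = 0.5 | r = 0.8 | Simulated range |
|---|---|---|---|
| 10% | 5.87 | 5.79 | 5.8-5.9 |
| 20% | 5.74 | 5.59 | 5.6-5.8 |
| 50% | 5.36 | 4.97 | 5.2-5.5 |

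The simulation (6,000 runs per scenario, Monte Carlo error about 0.02) shows slightly less shrinkage at 50%. Mixing scores from days with different means flattens the covariate slope. At 5% missing the simulated estimate is about 5.9. A Day 1 covariate with an arm-blind mean fill gives 6.0 throughout, on the assumption that no effect is present on Day 1.

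**Sensitivity.**
- At 20% missing, the estimate is 5.96-6.00 if no effect is present by Day 7, 5.8-5.9 if 10/40% is present by Day 3/7, and 5.5-5.7 if 40/80% is.
- A separate set of assumptions (Day 1 correlation 0.5, late-score correlation 0.7, half the effect in any late score) gives 5.80, 5.54 and 5.05 at 10%, 25% and 50% late.

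**Power and type I error under the current rule.** Simulated pooled power is at least 93.6%, or 92.6% if sicker subjects are the ones who miss Day 1. Up to 20% missing, the current and proposed rules differ by at most 1.3 power points, in the pooled test or the first step-down test. With equal timing across arms, type I error is 4.7-5.4%. It rises only if timing differs by arm: 6.7% with late baselines in 35% of placebo against 25% of active, and 10.4% if the outcome serves as its own baseline in 15% against 5%.

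**Why a fill rule is needed.** If Day 1 were required and subjects without it were dropped, power with no covariate gain would be 90.4% at 10% lost and 86.8% at 20% lost.

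**What the Day 1 window leaves.** If every Day 1 score already carried 10% of the effect, the estimate would be 5.5-5.7 under either rule with none missing. At 20% missing it would be 5.3-5.6 under the current rule and 5.6-5.8 with the fix.

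**The case against.** The strongest reply is that this is too small to matter. At 10% missing the bias is 0.1-0.2 points. The ANCOVA standard error is about 1.744 × √(1 − r²), or 1.51 at r = 0.5 and 1.05 at r = 0.8. The bias is then roughly 0.07 to 0.2 of one standard error, and no decision in the plan changes. This stands as a statement about size.

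Late baselines may also be rare. Subjects are ICU inpatients, the Day 1 window is wide, and each component is "graded on a 6-point scale from dependent to independent (0 to 5", so a dependent subject can still be scored. On the assumed split, the covariate-equals-outcome case is 5% of those missing Day 1: about 1 subject in 213 when 10% miss it. This stands too, and no rate can be read from the documents.

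The first-available rule already keeps everyone in the ITT analysis, and baseline windows are ordinary SAP content. Both are true. But the rule retains subjects by conditioning on post-treatment data, which an arm-blind fill does not. The supplementary imputation and tipping-point analyses do not change the covariate in the primary model.

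A reader might infer that the power claim fails. Holding the SD at 12 and cutting the effect to 5.62 (r = 0.5, half the effect present, 25% late) gives 89.7%. That is inconsistent: the correlation that causes the shrinkage also lowers the residual SD, to 12 × √0.75 = 10.39, and power is then 96.1%.

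**Conclusion.** The point holds as a small, correctable flaw in a stated rule. Followed literally, Section 10.2.4.1 adjusts some subjects for an on-treatment score and possibly for the endpoint itself, and this biases the CPAx effect toward zero if the drug acts early. Under the assumed ranges the loss is 0.1-0.2 points of 6 when 10% miss Day 1, 0.2-0.4 at 20% and 0.5-0.8 at 50%. It is essentially nil if no effect is present by Day 7. Every driver of these figures is an assumption.

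Two further inferences are not supported. Type I error inflation would need first-score timing that differs by arm; nothing in the documents suggests this, and blinding should make it unlikely. Nor does a Day 1 limit make every baseline a pre-treatment one or the estimate unbiased, because the Day 1 window extends to 24 hours after the first dose. The separate SAP may already deal with the matter.

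**What to change.** In the Synopsis, Section 10.2.4.1 and the SAP, define baseline CPAx as the last score before the first dose where one exists, and otherwise the score within the existing Day 1 window. State that a Day 3 or later score, or the endpoint score, is never used as baseline.

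In Section 10.2.2, state that a missing baseline is filled with the overall or stratum mean regardless of arm, so that no subject with an outcome leaves the ANCOVA. Report by arm the number filled and the number of baselines taken after the first dose.

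The cost is wording in three protocol places and the SAP, plus a short by-arm table; no visits are added. There are two downsides. Some covariates are imputed, and some Day 1 scores will still follow a dose, so the bias is reduced rather than removed. At 50% missing, the power difference in the first step-down test ranges from 3.7 points in favour of the change to 2.1 against. The reason to make the change is therefore a cleaner estimate, not a gain in power.
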